## PROTOCOL SUMMARY

Title	A Pilot Study Analyzing Preoperative Stereotactic Radiosurgery (SRS) With Gamma Knife® (GK) Icon™ for Brain Metastases
IND Sponsor	Not applicable
Principal Investigator	[name]
Study Population	Patients with radiographically confirmed solid tumor brain metastases.
Primary Objectives	
 
1. To assess feasibility of preoperative GK-SRS in patients with brain metastases treated with preoperative GK-SRS.
 
2. To assess local control in patients with brain metastases treated with preoperative GK-SRS.
 

Primary Endpoint	
 
1. Feasibility for this study will be defined as 50% of enrolled study subjects undergoing the surgical resection as per the protocol.
 
2. Measure the rate of local control at the resection cavity and the development of new metastatic brain tumors elsewhere in the brain as identified on post-treatment MRI of the brain.
 

Secondary Objectives	
 
1. To assess survival (CNS progression-free survival and overall survival) for patients undergoing preoperative SRS and surgical resection.
 
2. To document rates of leptomeningeal carcinomatosis for patients undergoing preoperative SRS and surgical resection.
 
3. To record incidence of radiation necrosis in patients undergoing preoperative SRS and surgical resection.
 
4. To document quality of life measures using preoperative Gamma Knife® and to compare to historically cited rates using postoperative Gamma Knife®.
 

Secondary Endpoint	
 
1. CNS progression-free survival and overall survival will be evaluated at six, 12, and 18 months after surgical resection.
 
2. Rates of leptomeningeal carcinomatosis using preoperative SRS will be documented and compared to historically cited rates for postoperative SRS.
 
3. Incidence of radiation necrosis will be measured by post-treatment MRI.
 
4. Quality of life measures will be collected and will be compared to historically cited rates.
 

Study Design	This is a single-arm, single-center, pilot study in which 10 completed patients with one to four brain metastases diagnosed on brain MRI within the past 30 days will be evaluated for study eligibility and enrolled as appropriate.
Study Intervention Description	Enrolled patients will receive SRS to all metastases followed by surgical resection of resectable metastases within one to 10 days following

	SRS. Pathologic specimens will be analyzed, and the patient will enter a standard pattern of surveillance (brain MRI every three months for two years).
Number of Subjects	Up to fifteen subjects will be enrolled in this study to attain ten completed subjects.
Estimated Time to Complete Enrollment:	Approximately two years.

## STUDY SCHEMA

## STUDY CALENDAR

Procedure	Screening 	Radiosurgery Delivery	Surgical Resection	Post-Surgical Resection Visit	Follow-up  (until 18-months from post-surgical resection visit) (18 months)
Study Day/Visit Day	Day – 30 to Enrollment	Day 1	Day 2 (+8 days)	1-month ±7 days from radiosurgery	Every 3 months ±14 days
Informed Consent	X				
AE Reporting	X	X	X	X	
Concomitant Medications	X	X	X	X	X
SRS		X		X	
Physical Exam 	X			X	X
Medical History	X				
ECOG Performance Status	X			X	X
Pregnancy Test (Serum or Urine) 	X				
Neurocognitive Testing 	X				
QOL Questionnaire 	X			X	X
MRI (Brain) 	X			X	X

1. All screening procedures must occur within 30 days prior to enrollment. Treatment must start within 14 days of enrollment.
2. If a subject has disease progression/relapse or subject withdrawal, then they will be followed as per follow-up requirements.
3. Including height and weight on screening. Temperature, HR, RR, BP and O2 sats or as per institutional standards at all timepoints.
4. For women of childbearing potential, a negative pregnancy test (serum or urine) must be obtained within 30 days prior to the first study intervention.
5. Neurocognitive testing: Multilingual Aphasia Examination Controlled Oral Word Associated Test (COWAT), Trail Making Test, Parts A and B (TMT), and Hopkins Verbal Learning Test-Revised (HVLT-R).
6. QOL Questionnaire: MDASI-BT, EQ-5D-5L.
7. MRI (brain) w/ contrast. Radiographic assessments will be completed as per RANO criteria (see Appendix 3).

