### **4.1 Subject Status**

Subject statuses throughout the trial are defined as follows:

- Prescreening: pre-consent (subject considering trial or study staff considering patient for the trial per institutional recruitment methods).
- Screening: period after consent, but prior to eligibility confirmation.
- Consented: consented, prior to eligibility confirmation.
- Eligible: the local investigator confirms all eligibly criteria apply.
- On study/enrolled: date eligibility is confirmed.
- On arm: date of enrollment.
- On treatment: first day treatment was given to the last day treatment was given.
- Off treatment: the last day treatment was given.
- On follow-up: from last day of treatment to the end of follow-up period.
- Off study: follow-up period completed, with no additional data gathered.
- Withdrawn: subject fully withdraws consent (i.e., refuses ALL follow-up, even survival) or is taken off study by the local principal investigator.

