#### **4.4 Screening Procedures**

Refer to the study calendar of events.

Visit procedures that were performed as standard of care prior to consent (without the specific intent to make the subject eligible for the trial), may count toward screening tests and eligibility if they are within the screening window.

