#### Inclusion Criteria

1. Voluntary written consent must be given before performance of any study-related procedure that is not part of standard medical care, with the understanding that consent may be withdrawn by the subject at any time without prejudice to future medical care.
2. English speaking.
3. Female or male subject's  $\geq$  18 years old at the time of informed consent.
4. Radiographically confirmed solid tumor brain metastases.
5. Criteria for surgical resection of at least one metastasis per neurosurgeon discretion.
6. Stereotactic radiosurgery candidate per radiation oncologist discretion.
7. A diagnostic MRI brain or CT head demonstrating the presence of one to four solid tumor brain metastases and lesion to be resected no more than 5 cm in any direction, performed within 30 days prior to stereotactic radiosurgery.
8. For known and unknown primary, ds-GPA estimated median survival no less than six months.
9. Surgical resection able to be performed within one to 10 days after radiosurgery.
10. Patients currently on cytotoxic chemotherapy or immunotherapy are eligible, not including anti-VEGF therapy.
11. Female subjects who:
  - a. Are postmenopausal for at least one year before the screening visit, OR
  - b. Are surgically sterile, OR

If they are of childbearing potential:

- i. Agree to practice one highly effective method and one additional effective (barrier) method of contraception, at the same time, from the time of signing the informed consent through four months after the last study Intervention (female and male condoms should not be used together), OR
- ii. Agree to practice true abstinence, when this is in line with the preferred and usual lifestyle of the subject. (Periodic abstinence [e.g., calendar, ovulation, symptothermal, post-ovulation methods] withdrawal, spermicides only, and lactational amenorrhea are not acceptable methods of contraception.)

CRC Initials: \_\_\_\_\_

Date: \_\_\_\_\_

Investigator/Enrolling Physician Initials: \_\_\_\_\_

Date: \_\_\_\_\_

12. Male subjects, even if surgically sterilized (i.e., status post-vasectomy), who:

- Agree to practice effective barrier contraception during the entire study treatment period from the time of signing the informed consent through and through four months after the last study intervention (female and male condoms should not be used together), OR

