### **Exclusion Criteria**

- Patients who received anti-VEGF therapy within six weeks prior to enrollment, as there is increased risk of fatal brain hemorrhage with surgical resection.
- Non-English speaking.
- Major medical illnesses or psychiatric impairments, which in the investigator's opinion will prevent administration or completion of the protocol therapy and/or interfere with surveillance.
- Patients with more than four brain metastases on MRI brain.
- Lesion to be resected is more than 5 cm in any dimension.
- Patients with leptomeningeal metastases documented by MRI or CSF evaluation.
- Previous whole-brain radiation therapy.
- Previous radiation therapy to the lesion to be resected.
- Planned adjuvant focal therapy including additional radiation therapy to the brain.
- Not a surgical candidate per neurosurgeon discretion.
- Not a stereotactic radiosurgery candidate per radiation oncologist discretion.
- Surgery unable to be performed between one to 10 days after radiosurgery.
- Women who are pregnant or nursing as treatment involves unforeseeable risks to the fetus or child.
- Patients who have a known or unknown primary and have an estimated median survival of less than six months per ds-GPA.

*"I have reviewed all inclusion and exclusion criteria and confirm the subject is eligible."*

---

(CRC Signature)

---

(Date)

---

(Investigator/Enrolling Physician Signature)

---

(Date)

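### The only required pregnancy test may predate consent, and so predate the contraception requirement; it should be done after consent

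*Combined protocol and SAP*

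**What the plan says.** The Study Calendar marks the pregnancy test in the Screening column only. Nothing is marked at radiosurgery, resection or any later visit. Footnote 4 sets the timing for women of childbearing potential: "a negative pregnancy test (serum or urine) must be obtained within 30 days prior to the first study intervention". It does not mention consent.

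Footnote 1 gives the general windows: "All screening procedures must occur within 30 days prior to enrollment" and "Treatment must start within 14 days of enrollment".

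Section 4.1 has two relevant definitions: "Screening: period after consent, but prior to eligibility confirmation" and "On study/enrolled: date eligibility is confirmed". By default, then, a screening test comes after consent.

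Section 4.4 makes an exception. Visit procedures "performed as standard of care prior to consent (without the specific intent to make the subject eligible for the trial), may count" toward screening and eligibility, provided they fall in the screening window. The pregnancy test is not carved out.

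In section 4.5, inclusion criterion 11 gives a woman of childbearing potential two options. Option i is two methods of contraception, "from the time of signing the informed consent through four months after the last study Intervention". Option ii is true abstinence consistent with her usual lifestyle, and it states no start date. The exclusion criteria bar "Women who are pregnant or nursing as treatment involves unforeseeable risks to the fetus or child". The coordinator and the enrolling physician each sign that all criteria are met.

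**The concern.** A pregnancy test and a contraception requirement work as a pair. The test shows that the woman was not detectably pregnant on a given date, and contraception covers the time from then until exposure. The pair leaves no gap only if contraception begins no later than the test. Under section 4.4 the order can be reversed: the test comes first, consent and contraception follow, and no further test is required before SRS.

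At stake is radiosurgery given during an unrecognised pregnancy to a woman who met the test and contraception rules exactly as written. The protocol treats fetal risk as serious enough to exclude pregnant women, and section 6.1.2 lists pregnancy among the serious adverse event outcomes.

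**Working it through.** The plan gives no figure of its own to reproduce. The check is date arithmetic on the stated windows.

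**Inputs.** Let T be the date of the test, C of consent, E of enrollment and S of SRS.

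- Footnote 4: S − T ≤ 30 days.
- Footnote 1: E − T ≤ 30 days, and 0 ≤ S − E ≤ 14 days.
- Section 4.1: C is no later than E.
- Section 4.4: T may be earlier than C if the test was standard of care and was not done to make the subject eligible.
- Criterion 11, option i: contraception is required from C.

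**Step 1: can T fall before C with every window met?** Yes. Because S is no earlier than E, a test that meets S − T ≤ 30 also meets E − T ≤ 30, so it lies inside the screening window that section 4.4 requires. No rule sets T ≥ C for a standard-of-care test.

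**Step 2: how long can the uncovered interval be?** Let c = S − C. Then C − T = (S − T) − (S − C) ≤ 30 − c, and it cannot be below zero.

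| Days from consent to SRS (c) | Longest test-to-consent interval, max(30 − c, 0) |
|---|---|
| 0 | 30 |
| 1 | 29 |
| 7 | 23 |
| 14 | 16 |
| 21 | 9 |
| 29 | 1 |
| 30 or more | 0 |

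The interval nears 30 days only if consent, enrollment and SRS almost coincide. Once consent is 30 or more days before SRS, no test done before consent can qualify. Footnote 1 alone would allow screening procedures up to 30 + 14 = 44 days before SRS. The calendar header can be read as a shorter span, but nothing here depends on the 44.

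**Step 3: what else would catch a conception in that interval?** The exclusion criterion applies whatever the test date, but it works only if the pregnancy is known. Medical history, physical examination and sign-off may reveal it, but none of them is a pregnancy test. No later test is scheduled.

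**Step 4: does requiring T ≥ C close the gap, and can it always be met?** With T ≥ C, the test-to-consent interval is zero or negative, so under option i the whole period from test to SRS lies under the contraception requirement. The rule can always be met in the Screening column: a test on the enrollment day follows consent and is at most 14 days old at SRS, inside the 30-day limit.

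**Step 5: is a tighter limit needed?** Not to close this gap. With a 14-day limit, a test t days before enrollment followed by SRS e days after enrollment fails whenever t + e > 14. For example, t = 3 and e = 12 gives 15, although 12 days is allowed by footnote 1. A slipped SRS date could then force a retest of an already enrolled woman, for which the protocol has no visit and no rule.

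**The case against.** The strongest reply is that pregnancy is excluded outright, that two people sign to confirm it, and that screening follows consent by default. Section 4.5 also binds staff to institutional eligibility procedures that are not in the documents and may require a current test. All of this is true, and it makes the path narrow. Harm needs a woman of childbearing potential, a standard-of-care test before consent, conception between that test and consent, and no recognition before sign-off. Option ii reduces the group further, since it describes abstinence as an existing way of life; the gap mainly concerns option i.

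The core point still stands. An exclusion depends on detection, and the one scheduled procedure meant to detect pregnancy can predate the conception. The section 4.1 definition does not close the gap, because section 4.4 expressly admits procedures done before consent. A routine test before surgery is not stated anywhere, and because resection follows SRS by one to 10 days, such a test could come after the radiation.

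A reader might infer two stronger things. The first is that the protocol permits pregnant women to be treated. It does not; a known pregnancy excludes the woman whatever her test date. The second is that the 30-day window is itself a defect and must be shortened. The documents do not show that: for a woman tested after consent under option i, contraception is already required from the test to SRS.

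**Conclusion.** The gap is real in the text and small in practice. Footnote 4 and section 4.4 together let a test done before consent be the only required test, while option i contraception begins at consent. The uncovered interval can be anything up to 30 days minus the days from consent to SRS.

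No probability can be put on it. The documents do not say how many women of childbearing potential will enroll or how often a standard-of-care test comes before consent. Enrollment is capped at 15, and the number affected may be zero. The conclusion assumes that the protocol text is the whole rule and that no unseen institutional procedure requires a later test.

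It would be wrong to infer any effect on feasibility, local control or the secondary endpoints: this is a subject-safety point only. It merits a change because the change is cheap and the possible harm is serious.

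**What to change.** Amend footnote 4 along these lines: *Women of childbearing potential need a negative serum or urine pregnancy test dated after the consent form is signed and no more than 30 days before SRS. The section 4.4 allowance for procedures done before consent does not cover this test.*

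The cost is one urine or serum test at screening for a woman whose only test predates consent. No new visit or calendar column is needed.

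The change reduces the risk but does not remove it, because any single test can miss a very early pregnancy, including one conceived shortly before consent. The sponsor may prefer a tighter limit, such as 14 days before SRS, but that is optional. It would need a rule for retesting when SRS slips after enrollment, and for handling an enrolled woman who then tests positive. If such a woman were removed, she would remain in the feasibility denominator, which section 2.3 bases on enrolled subjects.

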## LIST OF ABBREVIATIONS

AE	adverse event
ATC	Anatomical Therapeutic Chemical (Classification System)
AUC	area under the curve
CR	complete response
CRC	clinical research coordinator
CRF	case report form
CSF	cerebral spinal fluid
CT	computerized tomography
CTCAE	Common Terminology Criteria for Adverse Events
CTEP	Cancer Therapy Evaluation Program
CTMS	Clinical Trial Management System
DFS	disease-free survival
DLT	dose-limiting toxicity
DSMC	Data and Safety Monitoring Committee
DSMP	Data and Safety Monitoring Plan
ECOG	Eastern Cooperative Oncology Group
FCBP	female of childbearing potential
FDA	Food and Drug Administration
GCP	good clinical practice
ICH	International Conference on Harmonization
IND	investigational new drug application
IP	investigational product
IRB	Institutional Review Board
iwCLL	International Workshop on Chronic Lymphocytic Leukemia
IV	intravenous
LDH	lactate dehydrogenase
MCWCC	Medical College of Wisconsin Cancer Center
MedDRA	Medical Dictionary for Regulatory Activities
MRI	magnetic resonance imaging
MTD	maximum-tolerated dose
NCI	National Cancer Institute
NHL	non-Hodgkin lymphoma
ORR	overall response rate
PD	disease progression
PK	pharmacokinetics
PO	per os (by mouth, orally)
PR	partial response
QOL	quality of life
SAE	serious adverse event
SD	stable disease
SD	standard deviation

SRC	Scientific Review Committee
ULN	upper limit of normal
UP	unanticipated problem
UPIRSO	unanticipated problems involving risks to subjects or others

# 1 BACKGROUND

## 1.1 Brain Metastases: Epidemiology and Prognostic Factors

Brain metastases are the most common intracranial malignancy in adults and occur in up to 30 to 40% of cancer patients. Common primary etiologies include breast cancer, lung cancer, renal cell carcinoma, and melanoma. Symptoms depend on specific intracranial location, tumor volume, mass effect, tumor histology, and tumor-related hemorrhage. In general, prognosis after diagnosis of brain metastasis is poor; however, longer survival is now being observed with improved systemic therapies as well as earlier detection at more limited stages of neurologic involvement. Favorable prognostic factors include young age (<60 years), good performance status, female gender, solitary metastasis, absence of neurologic symptoms, and well-controlled primary disease with absence of metastasis outside the central nervous system.

## 1.2 Treatment Paradigm

Management is influenced by the number, location, and volume of brain metastases, as well as tumor histology, molecular markers, and recursive partitioning analysis (RPA) or graded prognostic assessment (GPA). Historically, approaches that have been investigated for treatment of one to four brain metastases include surgery alone, whole-brain radiation therapy (WBRT) alone, WBRT followed by surgery, surgery followed by WBRT, and surgery followed by SRS. Efficacy and timing of systemic treatment is an additional consideration for management of brain metastases depending on primary tumor histology.

## 1.3 Historical Perspectives

Early studies by Patchell et al. demonstrated superior local control and overall survival with the addition of surgery to WBRT, as well as superior local control and lower rates of neurologic-related deaths with the addition of WBRT to surgery for treatment of solitary brain metastases. A Cochran review published in 2005, however, did not confirm an overall survival benefit with the addition of surgery to WBRT. As SRS was developed, studies began evaluating WBRT with SRS boost. Collectively, these studies demonstrated a local control benefit using WBRT with SRS boost, as well as an overall survival benefit in patients with more favorable prognosis (favorable GPA, RPA Class 1, or solitary metastasis).

Due to concerns related to cognitive decline and quality of life measures with WBRT, studies on the use of SRS alone for a limited number of brain metastases ensued. These studies consistently reported superior local control and distant brain control with SRS plus WBRT compared to SRS alone, although conclusions related to overall survival were variable. Aoyama et al. reported an overall survival benefit using SRS with WBRT only in those with higher GPA scores, while Chang et al. reported a superior overall survival with SRS alone. Kocher et al., Brown et al., and Churilla et al. reported no difference in overall survival with the addition of WBRT. A meta-analysis by Soon et al. concluded no difference in overall survival, while an individual patient-data meta-analysis by Sahgal et al. concluded that SRS alone provides a survival benefit for patients <50 years of age. In addition, a recently published retrospective review comparing survival outcomes with SRS alone versus WBRT alone reported improved survival with SRS alone in patients with limited brain metastases from lung or breast cancer.

## 1.4 Recurrence Patterns

Lesions >3 cc in size often require surgical intervention to relieve mass effect and neurologic symptoms. Risk of recurrence at the resection cavity has been reported to be approximately 50%; consequently, postoperative radiation in the form of WBRT or SRS is frequently used to sterilize the surgical bed. Prospective data to support superiority of SRS versus WBRT in the postoperative setting is lacking, although there is some retrospective evidence to suggest that postoperative WBRT provides better intracranial local control than postoperative SRS for larger brain metastases but with no difference in OS. It should be noted that these comparisons are limited by the retrospective nature; in addition, optimal dose/fractionation schemes for postoperative SRS have not yet been determined with certainty.

## 1.5 Toxicity

Multiple studies report worsened cognitive decline and quality of life with the addition of WBRT to either SRS or surgery for a limited number of brain metastases. Given evidence for WBRT-related toxicity along with the lack of clear survival benefit with the addition of WBRT (and potentially a survival benefit with SRS alone in certain populations), the current trend for management of limited brain metastases now favors surgery (+/- postoperative SRS) or SRS alone with reservation of WBRT as a salvage option. A number of studies are now evaluating the use of SRS in patients with multiple (more than four) brain metastases. According to a recently published systematic review, SRS may be considered an option for patients with greater than four brain metastases provided the total tumor volume does not exceed 13 cc and no single metastasis is larger than 3 cc in volume. While postoperative WBRT carries the cognitive and quality of life toxicities discussed above, SRS carries the risk of CNS necrosis (up to 23%). In an effort to reduce the risk of radiation necrosis with SRS applied to larger volumes while retaining efficacy, different dose and fractionation schedules are under investigation.

